For MDA to be effective, it has been proposed that at least 80% coverage of the target population is necessary[18]. A TPE experience from China - targeting household members and neighbors of index case, as in this study – also suggests that high, generally >85% coverage, is needed to interrupt transmission [8]. There is no evidence to show that high coverage of TPE is feasible. Some challenges for high coverage of TPE versus RACD include willingness to take drug without knowing infection status and time it takes for staff to explain rationale for taking drugs. As high coverage is critical for effectiveness but is mainly an implementation challenge, a secondary goal of this study will be to determine the feasibility of achieving at least 80% coverage. We will also compare coverage to that achieved in RACD arm but we will not be powered to detect superiority of either approach (RACD coverage is expected to be at least 80%), or non-inferiority of TPE given the high sample size that would be required.

Other key aspects of feasibility will also be evaluated, including safety, acceptability, costs, and adherence. The ideal study to evaluate safety would involve a placebo arm. As the primary aim of this study is not to evaluate safety, and because there is already robust evidence to suggest that AL and DP are safe, including in asymptomatic individuals (e.g. with IPT), we will not include a placebo in the study but we will record serious adverse events in both the RACD and TPE arms. Acceptability of TPE vs. RACD will be evaluated through a qualitative assessment (the Acceptability Assessment) and quantitative analysis of refusal rates. The costs and relative cost-effectiveness of TPE vs. RACD will be evaluated by a detailed costing exercise. In order to evaluate a strategy that can be feasibly implemented by malaria programs, drugs will be delivered using a modified DOT strategy. Ingestion of the first dose of drug will be directly observed, and then the two subsequent doses will be left with the subject to self-administer at the same time on the subsequent 2 days. During up to 2 return visits, study staff may: document reported intake, make reminders, or observe ingestion of the drug. Adherence to DP will be measured by performing a pill count amongst residents of Target areas surrounding the first index case detected in each transmission season in each locality in the TPE arm.

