1. To determine the feasibility of obtaining at least 80% coverage of TPE, and compare coverage to that attained using RACD. Coverage will be defined as receipt of and adherence to the first dose of DP within initial visits by the study team in the TPE arm or receipt of a blood test in the RACD arm. Our **hypothesis** is that the coverage attainable for TPE will be at least 80%. We also hypothesize that coverage for TPE will be equivalent to RACD but we will not be powered to prove this hypothesis.
2. To measure adherence to a 3-day regimen of DP administered by modified DOT delivery system in the TPE arm. We hypothesize adherence will be 80%.
3. To compare potential serious adverse events associated with TPE and RACD. We will test the hypothesis that the risk of serious adverse events will not be higher in individuals receiving TPE versus RACD.
4. To compare the acceptability of TPE versus RACD as assessed by refusal rates and a qualitative assessment. We hypothesize that TPE will not be inferior to RACD in terms of acceptability and may be more desired.
5. To compare the costs of TPE versus RACD. We will test the hypothesis that the costs per event will not be higher for individuals receiving TPE compared to RACD and may be cost-saving.

4 Study design & methods

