4.4 Target Areas

The Target Area will be defined for TPE localities as all individuals residing within 200m of an index case that is detected in passive surveillance and resides in a TPE study locality, with individuals residing immediately beyond 200m included if a minimum of 30 individuals are not enrolled within 200m. This Target Area size was selected based on the existing RACD data whereby the mean number of individuals screened per index case was 32.

The Target Area will be defined for RACD localities as all individuals residing within 500m of an index case that is detected in passive surveillance and resides in a RACD locality. The malaria surveillance team will be trained to focus on maximizing coverage within the immediate 200m radius around the index case. This Target Area size was selected based on the current RACD policy in Swaziland.

Based on collected data on missing individuals, the estimated total number of individuals residing within 200m of an index case is 53. Thus, coverage to date for RACD has been 60%. However return visits do not typically occur at off hours (mornings and evenings). Moving forward, at least one return visit must occur during off-hours to ensure better capture and to maximize the sample size.

If a subsequent index case is reported in a target area (identified either through health facilities or RACD (all secondary cases identified in RACD become index cases)), the RACD intervention will not be repeated within 5 weeks (per current national policy). For the TPE arm, the intervention will not be repeated within 8 weeks or more than twice within the past year (DP drug insert recommends no repeat course within 8 weeks, and no more than 2 courses within one year).

Target Areas that reside on the border between two localities that were randomized to different arms will receive the intervention according to the locality randomization of the index case. For outcome measures, some contamination of the intervention arm's effect may occur if a neighboring locality is randomized to a different intervention. In the analysis we will adjust for distance from an index case for whom the surrounding area received TPE intervention. It will not be necessary to adjust for distance from an area where RACD was conducted because RACD is the current standard of care in all receptive areas of the country.

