The sample size for the Target Area assessments is estimated from incidence in the previous transmission season, and the expected drop in incidence among those in the TPE arm; resulting in an estimated 200 index cases total with 30 individuals screened or treated in the Target Areas around each case. With 200 index cases, we expect about 6000 encounters where individuals will receive a study intervention (either TPE or RACD). Based on preliminary RACD data, we anticipate 10% of these encounters will occur in individuals who previously received an intervention during the study period (repeated or overlapping Target Areas). For the follow-up end-line seroprevalence survey, these individuals will only be sampled once. Thus the effective sample size for the seroprevalence outcome measured in the Target Area population is expected to be 5400. Of note, the first index case for each Target Area will not be included since this person's malaria exposure occurred pre-intervention.

For the follow-up end-line infection prevalence survey, index cases will also be included as they will also be at risk for subsequent infection. Thus the effective sample size for the infection prevalence outcome measured in the Target Area population will be 5400 individuals screened plus 200 index cases, or 5600 individuals.

Adherence evaluation:

Adherence will be measured on a subsample that includes only the individuals in the Target Areas surrounding the first index case in each locality. We expect that 22 localities in the TPE arm will have at least one index case, and at least 30 individuals will be assessed for DP treatment per Target Area, for a total sample of 660 individuals.

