14.2 Outcome measures

Table 6. Outcome measures

Outcome	Indicator
Primary Aim	
Incidence	Cumulative incidence of all cases (Pf infection) identified by passive surveillance in the locality subsequent to the first reported case during the study period (not including additional cases found through RACD). Cases include both locally acquired and imported infections.
Secondary aims (effectiveness)	
Exposure (seroprevalence)	Seroprevalence to markers of recent exposure using ELISA in end-line survey samples taken from residents in Target Areas near the end of the study (expected mid 2017), excluding index cases detected through passive surveillance.
Infection prevalence	Prevalence of infection by LAMP and QTNASBA testing for gametocytes in LAMP positives in end-line survey samples taken from residents in Target Areas near the end of the study (expected mid 2017), including index cases detected through passive surveillance.
Time to first local post-intervention incident case	Time to first incident local case in the Target Area subsequent to the intervention. Target Areas that receive a repeat intervention will qualify to be included again at subsequent interventions.
Proportion of imported incident cases	Proportion of imported incident cases in the locality subsequent to the first reported case will be measured through passive surveillance. Additional cases found through RACD will not be included.
Transmission potential (by genotyping)	Microsatellite genotyping will be performed on samples collected from index cases as well as secondary cases.
Secondary aims (feasibility)	
Coverage	Proportion of persons residing within approximately 200m (TPE localities) or 500m (RACD localities) of the index case who consented to participate in the study and who completed the initial procedures for their study arm (finger prick for RDT in the RACD arm, initial dose of DP in the TPE arm)
Adherence	Proportion of persons who completed 3 days of therapy among all individuals initiated on DP in the TPE arm, as assessed by pill count
Prevalence of SAEs related to treatment	Proportion of subjects experiencing SAEs deemed possibly, probably, or definitely related to DP or AL, out of the total number of subjects enrolled
Acceptability	Qualitative assessment (See Section 10)
Cost	Cost per index case-level intervention, cost per case averted.

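### Coverage is measured over about 200 m in the TPE arm and 500 m in the RACD arm, so the planned between-arm comparison mixes the radius with the ability to reach people

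*Combined protocol and SAP*

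**What the plan says.** Section 14.2, Table 6, defines coverage as the "Proportion of persons residing within approximately 200m (TPE localities) or 500m (RACD localities) of the index case" who consented and completed the initial procedure of their arm (finger prick in RACD, first DP dose in TPE). Section 14.4 calculates this proportion by arm.

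The protocol intends a comparison. Section 2 states: "We will also compare coverage to that achieved in RACD arm but we will not be powered to detect superiority of either approach". Feasibility aim 1 in Section 3 adds: "We also hypothesize that coverage for TPE will be equivalent to RACD", again noting that this is unpowered. Section 2 also says that "RACD coverage is expected to be at least 80" per cent, without naming a radius.

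On field work, Section 6.2 has teams try to enrol everyone within the radius of their arm. For RACD, Section 4.4 adds: "The malaria surveillance team will be trained to focus on maximizing coverage within the immediate 200m radius around the index case". In Appendix G, an event in either arm may be coded complete with less than 100% reached once three visits are done and at least 30 people are enrolled. Codes 3 and 4 apply this to TPE and code 6 to RACD.

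The planning figures are in Sections 4.4 and 14.1. A mean of 32 people were screened per index case, "the estimated total number of individuals residing within 200m of an index case is 53", and coverage to date is therefore put at 60%. Section 14.1 plans for "200 index cases total with 30 individuals screened or treated in the Target Areas around each case".

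**The concern.** Aim 1 asks whether TPE reaches people as well as RACD does. With a different circle in each arm, the two proportions answer different questions. RACD teams are told to put the inner 200 m first, yet they are scored over a circle with 6.25 times the area. The same minimum effort (30 people, three visits) can close an event in either arm but is divided by different populations. A report could therefore credit TPE with better reach when much of the difference came from the radius.

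The planning figures do not settle which radius is meant. Section 1.3 describes the current 60% as a share of people in the Target Area, which for RACD is 500 m, while Section 4.4 derives it from residents within 200 m.

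**Working it through.** **Inputs.** From Section 4.4: 53 residents within 200 m, a mean of 32 screened per index case, 60% coverage to date. From Section 1.3: 8355 people screened, 263 index cases, RACD screening out to 500 m. From Section 14.1: 200 index cases with 30 people each. From Section 14.3: 66 TPE index cases and 1782 people treated. The population within 500 m is not given.

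**1. Reproduce the plan's figures.** 32/53 = 60.4%, against the stated 60%. As a cross-check, 8355/263 = 31.8 per index case, which matches 32 (the two counts end a month apart). Also 200 × 30 = 6000, 6000 × 0.9 = 5400, and 66 × 30 × 0.9 = 1782.

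The 60% divides everyone screened under a 500 m policy by the 200 m population. It is not RACD coverage as Table 6 defines it, and it overstates that figure if anyone lives between 200 m and 500 m.

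**2. Population within 500 m (assumption).** The area ratio is (500/200)² = 6.25, so the outer ring has 5.25 times the area of the inner circle. Let r be the density of the ring relative to the inner circle, taken from 0 to 1. Then N500 = 53 × (1 + 5.25r).

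**3. RACD score when both arms reach 80% within 200 m.** TPE then scores 80%, before any allowance for ineligibility. With q the share of the ring that RACD reaches, RACD scores (0.8 × 53 + q × 53 × 5.25r) / N500.

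| r | N500 | q = 0 | q = 40% | q = 80% |
|---|---|---|---|---|
| 0.1 | 80.8 | 52% | 66% | 80% |
| 0.25 | 122.6 | 35% | 57% | 80% |
| 0.5 | 192.1 | 22% | 51% | 80% |
| 1 | 331.3 | 13% | 46% | 80% |

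The gap depends on how the ring is worked. It disappears when the ring is covered as well as the inner circle.

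**4. A bias in the other direction.** Table 3 and Section 7.3 exclude some residents from DP, for example pregnant or breastfeeding women, infants under 9 months or under 7 kg, and people with fever. They are offered an RDT or a referral instead. Table 6 does not take them out of the TPE denominator, and they cannot receive the first dose that counts as coverage. If a share e of residents is ineligible and 80% of the rest take a first dose, TPE scores 0.8 × (1 − e). The documents do not give e, so the size of this effect is unknown.

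**5. Thirty people against 80%.** At 200 m, 30/53 = 57%. Reaching 80% there needs 0.8 × 53 = 42.4, or about 43 people per index case. Conversely, 30 people at 80% imply 30/0.8 = 37.5 residents, fewer than the 53 within 200 m. This mismatch is present at 200 m and affects the 80% TPE goal as much as the RACD expectation. Over 500 m, 30 people give 37% at r = 0.1 and 9% at r = 1.

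**The case against.** The strongest reply is that the radius is part of each strategy. RACD follows national policy at 500 m, and the study summary defines coverage as a share of the target population, so judging each strategy on its own Target Area is a fair feasibility question. The only coverage objective with a sample size is single-arm (TPE at 80%), and the protocol says openly that the comparison is unpowered. Field teams must attempt everyone within 500 m, with return visits to households short of full coverage, and Section 4.4 requires at least one off-hours visit to improve on 60%.

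Much of this stands. It justifies keeping a 500 m figure for RACD. It also defeats a stronger reading that a reader might infer from Table 6, namely that RACD must score lower by construction. In RACD the numerator, the denominator and the field target all extend to 500 m, so a larger circle does not by itself lower the proportion.

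It does not make the between-arm contrast interpretable. Lack of power concerns precision, whereas the different radii affect what is being estimated, and the estimate will still be reported against a hypothesis of equivalence.

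**Conclusion.** The concern holds in a limited form. The coverage comparison is not like with like, because the radius differs by arm and no common radius is defined. RACD is likely to score lower, given the 200 m focus and the completion rule, but this is not certain, and DP ineligibility pulls the TPE figure down by an unknown amount. The net direction is therefore not fixed. The 52% to 13% range against 80% is an illustration. It rests on an assumed ring density of one tenth to equal and on RACD reaching nobody beyond 200 m, which Section 6.2 does not intend.

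A reader might also infer that at least 80% RACD coverage is impossible because of the 500 m circle. The documents do not support that. The conflict with 30 people per index case already exists at 200 m and applies to both arms. Thirty is a planning average in the Target Area sample size and a minimum elsewhere (Sections 4.4 and 6.2, Appendix G), not a cap. The figures are inconsistent with one another; they do not show that 80% is out of reach.

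The point concerns a secondary feasibility outcome and leaves the primary incidence analysis untouched. It is still worth correcting, because the feasibility conclusion could mislead and the remedy is cheap.

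**What to change.** - Define the between-arm coverage comparison over residents within 200 m of the index case in both arms, for numerator and denominator alike. Report RACD coverage over 500 m separately, as a description of current policy.
- State how DP-ineligible residents count in the TPE arm.
- State how homes of unknown size, coded 999 in the household questionnaires, enter the denominator.
- In Section 2, give the radius to which the 80% RACD expectation refers. In Sections 1.3 and 4.4, say that the 60% baseline is people screened under a 500 m policy divided by residents within 200 m.
- Reconcile 30 people per index case with 53 residents and 80% coverage, for both arms.

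The cost is wording in Sections 2, 4.4, 14.2 and 14.4 and one subset defined by distance. Appendices H and J already record household GPS coordinates and member listings, and are completed for homes where nobody is present, so no new data are needed.

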Secondary outcomes	
 1) Seroprevalence by ELISA 2) Prevalence of infection 3) Proportion of imported to locally acquired incident cases 4) Time to first post-intervention incident local case 5) Transmission potential as measured by microsatellite genotyping 6) Coverage of the intervention: proportion of the target population that receives a finger prick in the RACD arm or that receives an initial dose of DP in the TPE arm (intention to treat analysis) 7) Adherence to DP in TPE arm. 8) Prevalence of serious adverse events (SAEs) related to treatment 9) Acceptance as evaluated by refusal rates and a qualitative assessment

Study personnel and institutions

Principal Investigators

[name]

Role in project: Principal investigator (PI)
 Deputy Lead, Operational Research, Malaria Elimination Initiative, UCSF Global Health Group
 Assistant Adjunct Professor, Pediatric Infectious Diseases, Department of Pediatrics, UCSF Benioff Children's Hospital
 University of California, San Francisco
 Assistant Professor, Pediatric Infectious Diseases, Department of Pediatrics, University of Texas Southwestern Medical Center
 [contact]
 Email: [contact], [contact]

[name]

Role in project: Co-PI
 Program Manager
 Swaziland National Malaria Control Program
 Swaziland Ministry of Health
 [contact]
 Email: [contact]

[name], PhD

Role in project: Co-PI
 Lead, Malaria Elimination Initiative, UCSF Global Health Group
 Associate Adjunct Professor, Department of Epidemiology and Biostatistics
 University of California, San Francisco
 [contact]
 Email: [contact]

Other Key Personnel and Collaborators

CHAI – Study team

[name]
 Study Role: Study Supervisor
 Regional Malaria Manager
 Clinton Health Access Initiative
 UCSF Global Health Group
 [name]
 [name]
 [contact]
 Email: [contact]

TBD

Study Role: Study Manager
 Malaria Program Manager
 Clinton Health Access Initiative
 UCSF Global Health Group

[name]
[name]
Phone Number: TBD
Email: TBD

[name]
Study Role: Research Associate
Malaria Research Associate
Clinton Health Access Initiative
[name]
[name]
[contact]
Email: [contact]

[name]
Study Role: Field Coordinator
Swaziland National Malaria Control Program
Study Lubombo office
[contact]

[name]
Study Role: Study physician

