If an individual cannot safely be given DP, that individual will not be given medication for presumptive treatment. Pregnant women and breastfeeding women will be excluded. All girls ≥ 10 years of age will also be asked about menses. Those who have had menarche but have not menstruated in the past 4 weeks will also be excluded. Infants < 9 months of age or < 7 kg will also be excluded. For infants and children unable to take tablets, drugs will be crushed, mixed with water and administered as a suspension. No more than two courses of DP may be given within a 12-month period. Additionally, a second course of DP should not be given within 2 months after the first course due to the long elimination half-life of piperazine. Other contraindications include: severe malaria, young children who vomit (electrolyte disturbances can increase QTc), heart problems or rhythm disturbances, kidney or hepatic insufficiency, recent treatment with certain medications (antiarrhythmics, neuroleptics, antibiotics, non-sedating antihistamines, antimalarial agents, and others (cisapride, droperidol, domperidone, bepridil, dephemanil, probucol, levomethadyl, methadone, vinca alkaloids, and arsenic trioxide).

Individuals who cannot safely be given DP will be tested by RDT using the *Pf*-specific First Response RDT during the intervention visit. At the time that blood is collected for RDT testing, the same finger prick will be used to generate a slide and dried blood spot. Four spots of blood will be collected for each DBS. A second finger prick will be used to collect microtainer blood samples from RDT-positive individuals. Subjects testing positive by RDT will be referred to the closest health facility for treatment with a drug that is safe for them according to national policy.

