4. Comparison of time to first post-intervention incident infection. We hypothesize that time to the first post-intervention index case within the Target Area will be longer for Target Areas receiving TPE compared to those receiving RACD. Analysis for this outcome will use a standard cox proportional hazards model to estimate the time to a subsequent incident infection among individuals in the Target Area.
5. Comparison of transmission potential using genotyping. Microsatellite genotyping will be used to measure transmission potential. DNA samples for genotyping will be collected from index cases and secondary cases. Based on malaria rates in Swaziland over the past three years, we expect approximately 200 index cases over the study period and 35 infections from the follow-up cross sectional survey (1.6% prevalence in the TPE arm and 0.4% in the RACD arm). We expect transmission potential to be lower in the TPE versus RACD arm. Relatedness of infections within Target Areas and within localities will be used as a surrogate for transmission potential.

Planned Analyses of Operational Feasibility and expected findings:

1. Coverage of the intervention. The numbers and proportion of the population completing finger prick testing (if RACD arm) or receiving at least the first dose of medication (if TPE) will be calculated by arm. The proportion of the individuals living in Target Areas around an index case that receive the TPE intervention is expected to be 80% with a 95% confidence interval from 76% to 84%.
2. Adherence to TPE. In the subsample of Target Areas surrounding the first index case in each locality assigned to TPE, we will assess adherence to the 3 day regimen of DP in TPE using pill count. We expect adherence to be 80%.
3. Safety of the TPE treatment. The number and percent of individuals experiencing an adverse event will be recorded by study arm. We expect that compared to RACD, TPE will be safely administered with few or no serious adverse events related to treatment, and no difference in SAEs compared to AL based on analysis of the adverse events report forms.
4. Acceptability of the intervention. See Section 10.
5. Costs per incident infection and per population. Detailed costing will be performed in 10 Target Areas per arm. We expect that costs per incident infection and per population for implementing the TPE intervention will be no higher than for RACD, the current standard of care.

15 Advisory Committee

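### At equal reach, the coverage rule scores TPE below RACD, because a DP-ineligible TPE resident who gets the required RDT counts as not covered

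*Combined protocol and SAP*

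**What the plan says.** Coverage is defined in four places, and all four credit different things in the two arms.

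- Study summary, secondary outcome 6: the share of the target population that "receives a finger prick in the RACD arm or that receives an initial dose of DP in the TPE arm", labelled intention to treat.
- Section 3, feasibility aim 1: "Coverage will be defined as receipt of and adherence to the first dose of DP within initial visits by the study team" for TPE; a blood test for RACD.
- Section 14.2, Table 6: "Proportion of persons residing within approximately 200m (TPE localities) or 500m (RACD localities) of the index case", who consented and completed their arm's initial procedures, spelled out as "finger prick for RDT in the RACD arm, initial dose of DP in the TPE arm".
- Section 14.4, operational feasibility item 1: finger-prick testing for RACD, or "receiving at least the first dose of medication (if TPE) will be calculated by arm".

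None limits the TPE denominator to residents eligible for DP.

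Table 3 applies the individual exclusions to the drug only; the person stays eligible for interview. Section 7.3 then gives these residents a procedure: "Individuals who cannot safely be given DP will be tested by RDT". Table 4 lists that RDT among the TPE enrollment activities. For RACD, Table 3 has no individual-level bar to the RDT; its only exclusion is an overlapping Target Area within 5 weeks.

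Sections 2 and 3 plan a between-arm comparison and state that it is not powered. Section 3 adds: "We also hypothesize that coverage for TPE will be equivalent to RACD".

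**The concern.** Table 6 describes coverage as completing the arm's own initial procedures, but its parenthesis leaves out one of the TPE arm's procedures. A TPE resident who cannot take DP and receives exactly what section 7.3 assigns is scored as a coverage failure. The same person, visited and tested in the same way in RACD, is scored as a success.

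The between-arm contrast therefore mixes two things: how well teams reach and enrol people, and how many residents are barred from DP. Section 2 treats high coverage mainly as an implementation challenge and names willingness to take drug and staff time as the obstacles. A safety exclusion is neither. At stake is whether equal field performance would be reported as lower TPE coverage, and whether the equivalence hypothesis would be judged on measures that are not like for like.

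**Working it through.** **The plan's own figure.** Section 14.3 gives 66 TPE index cases and 1,782 people. With 30 per case and 10% repeat encounters (section 14.1), 66 × 30 × 0.9 = 1,782, which reproduces. The 95% interval at 80% does not: 1.96 × √(0.8 × 0.2 / 1,782) = 0.0186, so 78.1% to 81.9%, against 77% to 83% in 14.3 and 76% to 84% in 14.4. Those widths would need design effects of (0.03/0.0186)² ≈ 2.6 and (0.04/0.0186)² ≈ 4.6, and none is stated for coverage. This is a separate inconsistency and does not affect what follows.

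**The same person in each arm.**

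| Resident | RACD | TPE |
|---|---|---|
| Can take DP, reached | RDT: covered | Dose 1: covered |
| Cannot take DP, reached | RDT: covered | RDT under 7.3: not covered |
| Not reached | Not covered | Not covered |

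Reading Table 6's consent clause as a limit on the denominator does not remove the asymmetry, since DP-ineligible residents also consent and enrol.

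**Size.** Let r be the share reached, equal in both arms, and e the DP-ineligible share, independent of reach. RACD coverage = r. TPE coverage = r(1 − e). Gap = r × e. The documents give no e; r = 85% and the values of e are assumptions.

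| e | RACD | TPE | Gap (points) |
|---|---|---|---|
| 5% | 85% | 0.85 × 0.95 = 80.8% | 4.25 |
| 10% | 85% | 0.85 × 0.90 = 76.5% | 8.5 |
| 20% | 85% | 0.85 × 0.80 = 68.0% | 17 |

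**Yardstick.** The ±3 or ±4 points in the plan is the precision of one TPE proportion, not of a difference. As an illustration, take RACD as the remaining 200 − 66 = 134 index cases, so 134 × 30 × 0.9 = 3,618 people, with 80% in both arms and the design effect of 2.6 implied above. The half-width for the difference is 1.96 × √(2.6 × 0.16 × (1/1,782 + 1/3,618)) ≈ 3.7 points. On these assumptions a gap from e = 5% is about the size of the sampling error, and one from e = 10% is clearly larger.

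**The 80% goal.** To score 80% over all residents, TPE must dose 0.80/(1 − e) of those eligible: 84.2%, 88.9% and 100% at e = 5%, 10% and 20%. Above 20% the goal cannot be met.

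**Can the fair figure be computed from the forms?** Appendix K item 22 records medication eligibility, and the Appendix J dashboards count dose 1. Neither shows an RDT field. Appendix I (RACD) has one at item 11, and section 7.1 assigns blood results to the RACD questionnaire and drug doses to the TPE one.

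**A fallback without the RDT.** Removing residents recorded as ineligible gives r(1 − e)/(1 − r × e), because eligibility is unknown for those not reached. At r = 85% this is 0.8075/0.9575 = 84.3%, 0.765/0.915 = 83.6% and 0.68/0.83 = 81.9%. The remaining gaps are 0.7, 1.4 and 3.1 points.

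**The case against.** The strongest reply is that the definition is deliberate. The summary labels it intention to treat, and sections 2 and 14.3 tie it to the 80% coverage thought necessary for mass drug administration. On that view, residents who cannot take DP are a real limit of presumptive treatment, and a lower TPE figure is a true difference between strategies. This stands for the single-arm goal: dose 1 over all residents is the right figure there. It does not make the between-arm contrast like for like. Intention to treat keeps everyone in the denominator; it does not require an arm-assigned procedure, once completed, to be scored as a failure.

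Second, the comparison is declared unpowered, and section 14.4 sets no equivalence margin or coverage decision rule. That limits the consequences. But lack of power concerns random error, whereas this is bias, and the two proportions will still be reported side by side.

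Third, a reader might infer that TPE coverage will come out lower in the trial. The documents do not support that. The radii are 200 m and 500 m, section 1.5 expects testing logistics to hamper RACD and drug-giving to ease first contact in TPE, and section 1.3 puts past RACD coverage at about 60%. The deficit holds only at equal reach.

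Finally, section 7.3 does not name fever or general illness among those given the RDT; Table 3 and section 7.4 refer such people to a health facility. Whether they are also tested is an inference. The example of a pregnant woman does not depend on it.

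**Conclusion.** The point holds as a statement about equal reach. The direction follows from the definitions alone. The size, r × e, rests on assumed values and on eligibility being independent of reach: about 4, 9 or 17 points at 85% reach and 5%, 10% or 20% ineligible.

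The harm is limited to a biased descriptive contrast and a biased reading of the equivalence hypothesis. A reader might go further and conclude that the coverage outcome is invalid or that a feasibility decision would fail. Neither follows. The main coverage target is TPE alone against 80%, which is correctly measured by dose 1 over all residents, and no decision hangs formally on the between-arm figure. It should still be changed, because the fair comparison cannot be recovered later if the RDTs given in the TPE arm are not recorded.

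**What to change.** In Table 6 and section 14.4, separate two figures, and align the summary and section 3 with them:

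1. **Against the 80% goal:** dose 1 of DP over all Target Area residents, unchanged.
2. **Between arms:** completion of the arm's own procedure. This is the RDT in RACD and, in TPE, dose 1 of DP or the RDT already required by section 7.3 for a resident recorded as DP-ineligible. Report the DP-ineligible share beside it, and state how residents referred for fever or illness are counted.

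Add an RDT-done and result entry to the TPE individual form (Appendix K) and to the TPE dashboard (Appendix J). If this cannot be done, report dose 1 after removing residents recorded as DP-ineligible, and say that it removes the gap only approximately because eligibility is unknown for those not reached.

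The cost is SAP wording, one form and tablet field, and one extra tabulation. No treatment rule changes.
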